Five patients will be enrolled into each stratum for evaluation of graft augmentation. If none of the five patients per stratum show any graft augmentation after one year, accrual to that particular stratum will be closed due to lack of efficacy. Patients will continue to be enrolled into other strata until criteria for five patients per stratum are fulfilled. If one out of five patients per stratum will meet listed criteria for graft augmentation, the next five patients may be enrolled to that stratum. If graft augmentation is seen in 1 of 5 or 2 of 10 cases in any stratum the strategy will be considered worthy of further investigation.

Since initiation of the study, it has been noted that stratum III encompasses a wide variety of diseases and therefore the majority of subjects enrolled have been to this stratum. As at least one subject has met the criteria for improved graft augmentation, the target enrollment for stratum III will be increased to 15 to accommodate this large group of patients.

If the infusion of purified CD34+ donor cells does not increase graft augmentation, patient will be removed from study and treated according to standard procedures.

There are no specific plans at this time to treat the patient with an additional boost of CD34+ cells if graft augmentation does not occur on study. However, this decision will be made on a per case basis as clinically indicated.

2a. Inclusion Criteria

To be eligible for this protocol, patients must have the following:

- 1. Primary immunodeficiency (e.g. SCID, Wiskott-Aldrich and/or other more rare conditions), or a bone marrow failure syndrome with prior allogeneic stem cell transplant.
- 2. Waning donor chimerism or immune function that is inadequate to correct their disease or clinical condition, for which primary transplant was given, as determined by their attending physician.
- 3. Available primary donor.
- 4. Must not have other organ dysfunction deemed by the attending physician to preclude this procedure.

- 5. Age < 35 years at time of transplant
- 6. One of the following must be true:
 - Patients must have evidence of persistent or recurrent immunodeficiency or thrombocytopenia.

-OR-

• Primary immunodeficiency disease with known potential to progress to malignant condition if untreated.

-OR-

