Infusional Toxicity: Infusion of stem cells could result in infusion reaction presenting as shortness of breath, fever, or anaphylaxis. To reduce the risk of infusion reaction, CD34+ stem cells will be highly T-cell depleted. While we have the expectation of a low occurrence of this toxicity, we will monitor for the frequency and characteristics of infusion related toxicities.

Statistical Analysis

We expect the frequency of adverse events in this study to be low (likely less than 5% events). We will therefore use all 45 patients to determine the frequency of adverse events as our ability to correctly define the frequency of events in any one stratum of 10 cases is low.

Descriptive statistics will be compiled on responding and non-responding cases, including patient and graft characteristics that might influence response. It is recognized that this portion of the analysis is exploratory due to the small sample size, but these data will be used to inform the design of future studies.

Stopping Rules

The primary endpoint of this study is qualitative graft augmentation. Five patients will be enrolled into each stratum for evaluation of graft augmentation. If none of the five patients per stratum show any graft augmentation, accrual to that particular stratum will be closed due to lack of efficacy. Patients will continue to be enrolled into other strata until criteria for five patients per stratum are fulfilled. If one out of five patients per stratum will meet listed criteria for graft augmentation, an additional five patients may be enrolled to that stratum.

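### One stratum's result can carry the verdict for the whole strategy, including strata closed with no responder among five

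*Combined protocol and SAP*

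**What the plan says.** The enrolment plan just before 2a. Inclusion Criteria works one stratum at a time:

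- Start: "Five patients will be enrolled into each stratum for evaluation of graft augmentation".
- Closure: with no responder among the five, "accrual to that particular stratum will be closed due to lack of efficacy".
- Expansion: "If one out of five patients per stratum will meet listed criteria for graft augmentation, the next five patients may be enrolled to that stratum".
- Exception: because "stratum III encompasses a wide variety of diseases", most subjects have entered it, and "the target enrollment for stratum III will be increased to 15".

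The conclusion is not framed in the same way. It reads: "graft augmentation is seen in 1 of 5 or 2 of 10 cases in any stratum the strategy will be considered worthy", and the words after that make clear that what is meant is further study. The subject of that sentence is the strategy, and the trigger is any stratum.

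Under 7. Data Analysis/Statistical Considerations, Stopping Rules repeats the closing and expansion rules but not the verdict. For efficacy, Statistical Analysis says that "Descriptive statistics will be compiled on responding and non-responding cases" and calls this exploratory. The available text states no uninteresting or target response rate, no error rate, no response estimate or interval by stratum, and no threshold for stratum III at 15.

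**The concern.** Failure is local and success is global. A stratum with no responder among five is closed on its own account, yet it does not count against the overall verdict. A single responder elsewhere is enough, on the literal wording, to call the strategy worth pursuing without restriction to the group in which the response was seen.

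Two things are at stake. The first is scope: a result from one stratum can be read as support in strata that the same plan closed for lack of efficacy. Within stratum III, a response in one diagnosis can likewise stand for a mixed group. The second is frequency: each extra stratum is another chance to reach the overall verdict.

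The plan is more cautious about safety. It pools all 45 patients for adverse events because "our ability to correctly define the frequency of events in any one stratum of 10 cases is low". The efficacy verdict can rest on five.

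**Working it through.** **Inputs**

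- First stage of 5 per stratum, closure at 0 of 5, and the two limbs 1 of 5 and 2 of 10: enrolment plan.
- Ordinary full stratum of 10: Statistical Analysis. Stratum III at 15: enrolment plan. Target accrual of 45: section VIII.
- Number of strata k: the pages that define the strata were not available to this review. Since 45 = 15 + 3 × 10, four strata fit. This is an inference, not a stated figure.
- True response rate p: not stated, so it is varied from 1% to 10%. The only 5% in the text is an expected adverse-event rate.
- Five evaluable patients in every stratum are assumed. VI.5 replaces subjects who do not complete six months of follow-up.

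The plan states no chance of reaching the verdict, so there is no figure to reproduce.

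**Literal rule.** Because 0 of 5 closes a stratum, the 2-of-10 limb adds nothing when the rules are applied in sequence. One stratum passes with probability 1 − (1 − p)^5. At least one of k passes with probability 1 − (1 − p)^(5k).

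| True rate | One stratum | Any of four |
|---|---|---|
| 1% | 1 − 0.99^5 = 4.9% | 1 − 0.99^20 = 18.2% |
| 5% | 1 − 0.95^5 = 22.6% | 1 − 0.95^20 = 64.2% |
| 10% | 1 − 0.90^5 = 41.0% | 1 − 0.90^20 = 87.8% |

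With three strata at 5% the chance is 1 − 0.95^15 = 53.7%.

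**Gate reading (at least 1 of 5 to continue, then at least 2 of 10).** One stratum passes with probability P(X ≥ 2) + P(X = 1) × P(Y ≥ 1), where X and Y are the responders in the first and second five. At 5% this is 0.0226 + 0.2036 × 0.2262 = 0.0687, or 6.9%. For any of four it is 1 − (1 − 0.0687)^4 = 24.8%. At 10% the two figures are 21.6% and 62.2%.

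Those figures put all four strata at 10. With stratum III at 15 and p = 5%, the chance that any stratum passes is 27.6% if 2 of 15 is enough and 21.4% if 3 of 15 is needed.

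**How often the verdict would coexist with a closed stratum.** On the literal rule at 5% with four strata, all four pass with probability 0.2262^4 = 0.3%. The verdict is therefore reached with at least one stratum closed at 0 of 5 in 64.2% − 0.3% = 63.9% of trials. At that rate, almost every overall verdict would extend to a closed stratum.

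**What one stratum can show.** Exact (Clopper-Pearson) 95% intervals:

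- 1 of 5: 0.5% to 71.6%
- 2 of 10: 2.5% to 55.6%
- 0 of 5: 0% to 52.2%

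**The case against.** The strongest reply is that this is a screen. The sentence ends by recommending further investigation, not by claiming efficacy, and a permissive screen is an ordinary choice in a small study without randomization. That stands, and it limits the weight of the point.

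A reader might infer that the plan has a false-positive rate of 64%. The documents do not support that. The figure needs a 5% response rate that they never give and a number of strata that is inferred; from 1% to 10% it runs from 18.2% to 87.8%. They also do not say what rate is uninteresting. Entry requires waning chimerism or inadequate immune function, and the chimerism criterion requires doubling at 3, 6 and 12 months. If spontaneous response is near zero, a true 5% may be real activity. The immune-function criterion sets no minimum improvement, so the background rate is unknown.

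Nor are the several strata the only cause. At 5%, the 1-of-5 bar alone passes a single stratum 22.6% of the time; having four strata accounts for the rise to 64.2%. Enrolment has also been concentrated in stratum III, so fewer than four strata may reach five patients.

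Finally, closure is by stratum, so the authors may have meant the verdict by stratum too. That reading is possible, but it is not what the words say. Nothing in the plan states that a positive stratum will be reported as support for strata that failed; the wording permits it.

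It is also tempting to say that stratum III has already met the overall verdict, since at least one subject there has responded. The text does not say whether that subject was among the first five.

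**Conclusion.** The point holds as one of scope. Taken literally, a response in one stratum supports the whole strategy, including strata closed at 0 of 5, and the number of strata tried raises the chance of that verdict. This is true on either reading of the two limbs and at every response rate examined.

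Its size cannot be fixed from the documents. It depends on the assumed true rate, on the inferred four strata, on each stratum reaching five evaluable patients, and on whether 1 of 5 is a final criterion or only a gate. The figures illustrate how a screening rule behaves; they are not error rates of an efficacy test. The clarification is worth making because this sentence is the only efficacy conclusion that the available text specifies.

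**What to change.** - End the verdict sentence with the words 'in that stratum'.
- Report responders over infused, with an exact 95% interval, for every stratum, including those closed early. Using infused patients keeps in the denominator those replaced under VI.5.
- List stratum III responses by diagnosis.
- State beside the verdict how many strata were tried.

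When the sentence is revised, it would help to say whether 1 of 5 is a final criterion or a gate, and what threshold applies to stratum III at 15, since the figures above turn on both.

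The cost is a change of wording, one small table and a narrower claim. No patients are added. The change limits what a passing stratum can be said to show. It does not reduce the chance that at least one stratum passes, which stays at 64.2% under the literal rule with four strata and a 5% true rate.

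### Stratum III goes to 15 on a responder condition that the five-patient rule already guarantees, so no working efficacy check remains after the first five patients

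*Combined protocol and SAP*

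**What the plan says.** The enrolment plan (before 2a, Inclusion Criteria) sets one efficacy check per stratum. It starts with "Five patients will be enrolled into each stratum for evaluation of graft augmentation". The lower branch is "If none of the five patients per stratum show any graft augmentation after one year, accrual to that particular stratum will be closed". The upper branch is "If one out of five patients per stratum will meet listed criteria for graft augmentation, the next five patients may be enrolled" in that stratum. The conclusion line follows: "If graft augmentation is seen in 1 of 5 or 2 of 10 cases in any stratum the strategy will be considered worthy" of further study.

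The next paragraph changes stratum III only. It first gives breadth and accrual as background: "it has been noted that stratum III encompasses a wide variety of diseases and therefore the majority of subjects enrolled have been to this stratum". It then says "As at least one subject has met the criteria for improved graft augmentation, the target enrollment for stratum III will be increased to 15", with the purpose of making room for this large group. It gives no denominator for the responder, does not mention patients 6-10, and sets no line at 10 or 15 for the enlarged stratum.

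The Stopping Rules under Data Analysis/Statistical Considerations repeat closure at 0 of 5. At 1 of 5 they allow that "an additional five patients may be enrolled to that stratum". They go no further than ten patients.

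**The concern.** A staged design protects patients and conclusions only if each stage can fail. Here the stated condition for the third block of five repeats the one that opened the second block. If patients 6-10 all fail, the condition still holds. The other reason, accrual, is not an outcome.

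This matters most in stratum III. By the plan's own account it takes most of the enrolment and mixes many diseases, so a single responder says little about the rest. No other planned efficacy check stands behind it. Section VI.7 provides for no DSMB or medical monitor, and section VIII names only full accrual and toxicity as reasons to close. At stake are up to five further patients in a stratum that may have 1 responder in 10, and a favourable conclusion for that stratum resting on one early responder.

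**Working it through.** **Inputs from the documents.** First stage 5; close at 0 of 5; continue at 1 of 5, read as at least 1; conclusion line 1 of 5 or 2 of 10; stratum III target 15; total target 45 (section VIII). The size of 10 before the change follows from 5 + 5 and from the Statistical Analysis paragraph, which speaks of a stratum of 10 cases.

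**The plan's own figures.** No alpha, power, null rate or target rate is stated for any stratum, so there is no error rate to reproduce. The total of 45 equals 3 × 10 + 15 if there are four strata. The list of strata is not in the text available here, and 3 × 15 also gives 45, so this is only a consistency check.

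**Step 1: what the condition screens.** A stratum properly past five has at least 1 responder. Hence P(at least 1 responder by patient 10 | past five) = 1 at any response rate. This step needs no assumption about the rate.

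**Step 2: how often a stratum past five stands at 1 of 10.** Let p be the true response rate (an assumption), with independent patients.

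- P(past five) = 1 − (1 − p)^5
- P(past five and exactly 1 of 10) = 5p(1 − p)^4 × (1 − p)^5 = 5p(1 − p)^9
- Share at exactly 1 of 10 = second ÷ first
- P(past five and at least 2 of 10) = first − second

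At p = 0.05: 1 − 0.95^5 = 0.226; 5 × 0.05 × 0.95^9 = 0.158; ratio 0.697; difference 0.069.

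| Assumed p | Past five | Past five, exactly 1 of 10 | Share at 1 of 10 among those past five | Past five, at least 2 of 10 |
|---|---|---|---|---|
| 5% | 22.6% | 15.8% | 69.7% | 6.9% |
| 10% | 41.0% | 19.4% | 47.3% | 21.6% |
| 20% | 67.2% | 13.4% | 20.0% | 53.8% |
| 30% | 83.2% | 6.1% | 7.3% | 77.1% |
| 40% | 92.2% | 2.0% | 2.2% | 90.2% |

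As written, the chance that stratum III becomes eligible for patients 11-15 is the second column. If 2 of 10 were also required, it would be the last column.

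**Step 3: the 'or'.** No stratum reaches 10 without 1 of 5, and 1 of 5 already satisfies the conclusion line. P(favourable conclusion) therefore equals P(at least 1 of 5), the second column, and the 2-of-10 arm never alters the verdict. With a stage-specific rule applied to strata filled to 10, it would be the last column.

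**Step 4: what one responder means at each size (exact 95% intervals).** 1 of 5 is 20% (0.5% to 71.6%); 1 of 10 is 10% (0.3% to 44.5%); 1 of 15 is 6.7% (0.2% to 31.9%). Both arms of the conclusion line are 20%, and the same fraction at 15 would be 3 of 15. The plan does not say this.

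**The case against.** Several stronger readings are tempting, and the documents do not support them.

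- **That the expansion bypasses a 2-of-10 enrolment gate.** There is no such gate. The 2-of-10 figure belongs to a conclusion line with 1 of 5 as an alternative, so a stratum at 1 of 5 then 1 of 10 has breached nothing. The shares in the table measure distance from a figure that the plan gives but does not enforce.
- **That one response alone drove the change.** Breadth and accrual come first in the text, and the response works as a permissive condition.
- **That stratum III had only one responder.** The wording is a lower bound. The true count may be well above 2 of 10.
- **That every stratum can grow to 15.** Only stratum III is enlarged.

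The harm is also limited. The step adds at most five patients. Suspension for unexpected grade 4 events and for GVHD of grade II or above continues throughout. The pooled 45 serves adverse-event frequency, not the efficacy verdict. At true rates of 30% to 40% a check at 10 would rarely bind.

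All of this stands. It does not remove the central point: as written, nothing after the fifth patient can change the efficacy decision for stratum III, and the count behind the enlargement is not given.

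**Conclusion.** The concern holds in this limited form. The responder condition for patients 11-15 adds no efficacy screen, the 'or' leaves the 2-of-10 figure without effect, and the Stopping Rules omit the step to 15.

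The logical part assumes only that the five-patient rule was applied with outcomes in hand. The documents do not say how many stratum III patients had been evaluated, or whether the responder was among the first five. If the rule was not fully applied, the condition could be looser than 1 of 5.

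The size depends on the unknown response rate. It is large if the infusion seldom works (70% of strata past five stand at 1 of 10 at a 5% rate) and small if it often works (2% at a 40% rate). The documents do not show that stratum III is failing. They leave a reader unable to tell. This should be corrected, because it decides what the largest stratum can conclude.

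**What to change.** 1. State stratum III responders over evaluated patients at the time of the change.
2. Replace the 'or' with one rule per stage: at least 1 of 5 to continue; at least 2 of 10 to conclude that the strategy merits further study.
3. Base the stratum III decision on its first 10 patients counted under the six-month replacement rule (section VI.5). Report patients 11-15, and all 15 together, as supplementary estimates with exact confidence intervals.
4. If patients 11-15 are not yet enrolled, consider opening them only at 2 or more responders among the first 10.
5. Copy the rule, including the step to 15, into the Stopping Rules.

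Items 1, 2, 3 and 5 need a short amendment and no new data. Item 4 is a genuine trade-off. Accrual to stratum III may have to wait for outcomes, up to a year on the plan's own closure rule, and five places may go unfilled, taking the total from 45 to 40 if all else fills. Among strata past five, it would stop 20% at a true rate of 20%, 7% at 30% and 2% at 40%. If the sponsor prefers to expand for accrual alone, the plan should say so, and items 2 and 3 still protect the conclusion.

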• Debilitating secondary disease known to be a consequence of inadequate immune response to known agent or pathogen, uncontrollable by other available medical therapies (e.g. third patient described on page 5).

2b. Exclusion Criteria

- 1. Absence of an available original donor
- 2. Failure to sign consent form, or inability to undergo informed consent process
- 3. Pregnant or lactating female
- 4. Uncontrolled GVHD

3. **Randomization**

Not applicable.

4. **Procedures**

Pre-infusion evaluation:

Patients enrolled on this protocol will be evaluated for disease status and organ function prior to stem cell infusion, required testing as follows:

- 1. Peripheral Donor Chimerism Studies
- 2. CBC with differential and platelets
- Immunological studies including but not limited to absolute numbers of all lymphocyte subsets NK, T, B lymphocyte function, proliferation to mitogens, immunoglobulins
- 4. Urine pregnancy tests for girls of childbearing age
- 5. Renal and liver function tests

Treatment Plan:

Treatment Scheme

This treatment will involve these steps:

- 1. Pre-infusion evaluation
- 2. Collection of Granulocyte Colony Stimulating Factor (GCSF) mobilized peripheral blood stem cells from same donor used for first transplant as per standard procedures
- 3. Selection of CD34+ stem cells and T-cell depletion using CliniMACS
- 4. Infusion of stem cells into recipient
- 5. Continue monitoring

Schedule*:

Pre-infusion	Clinic visit and evaluation of peripheral blood counts	
Day 0	Infusion of CD34+ selected stem cells	
Day 7	Clinical assessment	
3, 6, 12	Clinical assessment	
months and	Donor chimerism studies	
then yearly for	Immunological studies	
up to 3 years		
post infusion		

*For details see Required Observations, page 10.

Additional testing such as disease specific markers (CD132, WASP) or more frequent testing might be needed at attending physician discretion if indicated by patient's clinical condition.

Preparative therapy:

No preparative therapy or additional immunosuppressive therapy will be given in preparation to stem cell infusion.

Stem Cell Infusion:

Stem Cells will be administered per standard institutional protocols.

Immune Suppression after stem cell infusion:

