Viable CD3+/Kg	Flow Cytometry	≤ 5 x 10⁴/kg
Gram Stain	Gram Stain	Negative

Safety of Product

Unrelated donor evaluation will be completed per the relevant unrelated donor registry standards (additional testing at discretion of physician and NMDP/registry donor center).

Related donors will be evaluated per donor standard operating procedures. As part of this research we will collect clinical data to ensure eligibility.

Product testing

The following tests will be performed on each product produced to assure product safety, purity, and potency:

Pre CD34 Selection (T cell Depletion): Total nucleated cell count Viability CD 34+ cells/kg of recipient CD 3+ cells/kg total volume collected sterility (bacterial and fungal culture)

Post CD34 Selection (T cell Depletion): Total nucleated cell count Viability Viable CD 34+ cells/kg of recipient Viable CD 3+ cells/kg of recipient total volume for infusion endotoxin assay (Limulus Amebocyte Lysate Test or equivalent) stat gram stain sterility (bacterial and fungal culture)

Culture of the product:

If the culture of the product (either fungal or bacterial) becomes positive following infusion of the cells, antibiotics or antifungal medications will be administered to the recipient. The patient/guardian and treating physician will be informed.

Endotoxin testing:

An endotoxin assay will be performed on the post-selection product within 24 hrs of infusion, and the patient's physician will be notified if more than 5 EU/kg was infused into the recipient.

Required Observations:

1. Clinical Assessment

An assessment of the patient will be done on Day 7 (+/- one day), at three months (+/- four weeks), and at or around six and twelve months. This will include a complete physical exam and CBC.

2. Donor chimerism studies

Peripheral blood donor chimerism studies will be performed only for subjects for whom the CD34 product has been provided for inadequate donor chimerism. Chimerism studies will be performed at or around three, six and twelve months, then annually for up to 3 years after the stem cell infusion. Thereafter, chimerism studies will be performed as clinically indicated. Donor chimerism analysis will be done on peripheral blood using standard FISH or VNTR analysis.

3. Immunological studies

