Graft versus host disease (GVHD): GVHD is unlikely as a low number of T-cells will remain after cell selection and the recipients already have stable mixed chimerism with cells from their donors. Acute GVHD can cause a skin rash, liver dysfunction, and/or enteritis, and is potentially fatal. Chronic GVHD is a multi-organ autoimmune disease, which may resolve over several months or years or lead to death, commonly from infection.

2. Precautions that will be taken to monitor and avoid the above mentioned risks, discomforts, and inconveniences, including methods for detecting adverse events

Infusion reactions: The risk of transfusion reaction will be minimized by appropriate testing of the donor and products, and by use of pre-medication. Pre-medications will be given according to standard practice. Patients will be monitored according to CCHMC guidelines during stem cell infusion for any infusion reactions. To reduce the risk of product infusion, CD34+ stem cells will be highly T-cell depleted. Should an infusion reaction occur it will be treated with supportive therapy according to standard transplant procedure.

Graft versus host disease: The risk of developing a new case of GVHD is anticipated to be very low. No GVHD prophylaxis will be given. Any occurring

GVHD would be treated according to accepted standards.

3. The method of monitoring study conduct.

All grade 3 or greater adverse events occurring during this study will be recorded on the case report forms. The principal investigator will review each event and assess its relationship to study events as to whether the event is unrelated, unlikely related, possibly related, probably related, or definitely related to the study device. The CTCAE Version 3.0 will be used to evaluate these adverse events.

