This population of patients, by nature of their various disease/conditions and due to effects from the original allogeneic hematopoietic stem cell transplantation (with a full preparative regimen), often continue to experience disease and therapy-related complications and are frequently hospitalized for observation and/or treatment of these conditions. As these patients do not receive any preparative therapy as participants in this study, the risk of study-related toxicity is expected to be minimal. Consequently any serious adverse events, as defined by the IRB guidelines, that are determined to be possibly, probably or definitely related to the study device will be reported according to IRB reporting regulations. However, serious adverse events determined to be related to the patient's underlying disease/condition or to the first transplant procedure, including hospitalizations or prolongation of hospitalizations resulting from such events, will not require expedited reporting to the IRB. These events will be reported annually with the progress report. Please note that for the purpose of this study we will exclude the report of hematologic toxicities, as these subjects, by virtue of their underlying disease and/or condition may present with baseline hematologic toxicity.

Although these subjects will be followed on study for up to 3 years post infusion, all adverse events (as described above) will be captured for the first 30 days post stem cell infusion. Thereafter, only related adverse events will be recorded on case report forms.

4. Methods for maintaining data quality and confidentiality

Data quality is monitored and audited by the Center for International Blood and Marrow Transplant Research and the National Marrow Donor Program. Confidentiality is maintained as per section VI.

5. An assessment of accrual (timely enrollment) and the handling of dropouts.

Accrual assessment will be evaluated by the principal investigator with the annual progress review. Subjects who do not complete a full six months of follow up will not be counted in the total stratum accrual and will be replaced.

6. Risk assessment recommendation

- Minimal risk but with direct benefit to participants
- Minimal risk but without direct benefit to participants

More than minimal risk but with direct benefit to participants

More than minimal risk but without direct benefit to participant

7. Data and Safety Monitoring Plan

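### Non-responders are removed from the study with no stated safety follow-up, so whether late related events and GVHD are observed depends on the efficacy result

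*Combined protocol and SAP*

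**What the plan says.** - **Removal.** The enrolment plan, just before 2a Inclusion Criteria, says that if the infusion "does not increase graft augmentation, patient will be removed from study" and then managed by standard procedures. It gives no time for this and no later data collection. The next paragraph leaves a further boost to case-by-case decision.
- **Follow-up and event capture.** Section VI.3 reads "Although these subjects will be followed on study for up to 3 years post infusion", without an exception for non-responders. All qualifying adverse events "will be captured for the first 30 days post stem cell infusion". The next sentence is "Thereafter, only related adverse events will be recorded on case report forms". Section VI.7 repeats the late rule and ties it to subjects who are on study.
- **Safety denominator.** Statistical Analysis (section 7) pools all 45 patients for adverse-event frequency, because a stratum of 10 is too small. It expects a rate below 5% and gives no time window.
- **GVHD.** Section VI.1 says: "Chronic GVHD is a multi-organ autoimmune disease, which may resolve over several months or years or lead to death". The Stopping Rules suspend the study for documented GVHD of grade II or above, with no time limit.
- **Visits.** The Schedule under Procedures lists clinical assessment at 3, 6 and 12 months and "then yearly for" up to 3 years. Required Observations item 1, to which the Schedule refers for details, lists it on Day 7, at three months "and at or around six and twelve months", and stops there.

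**The concern.** Treatment is a single infusion. Removal from the study therefore cannot mean only that study treatment stops; read plainly, it ends study visits and event capture. From then on, whether a patient is observed for late harm depends on whether the infusion worked.

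This matters because toxicity is the first objective in section I, and the hypothesis there claims minimal or no therapy-related toxicity or GVHD. Late GVHD in a removed patient might not be documented on study and so might not trigger the suspension rule. Section VI.7 provides no DSMB or medical monitor, so the principal investigator's view of the data is the only safeguard inside the study.

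**Working it through.** **1. The texts side by side.** Response is assessed at 3, 6 and 12 months (Primary Endpoints), and a stratum is judged after one year (enrolment plan). Removal could therefore fall at any of these times. Before it, responders and non-responders are observed alike. After it, only responders are on study, and late capture applies to subjects on study (VI.7). First-30-day capture ends before the first response assessment at 3 months, so infusion toxicity is largely untouched.

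**2. The plan's own figure.** The safety denominator is 45, which is also the accrual target in section VIII. With 15 in stratum III and 10 in each other stratum, 15 + 10 × 3 = 45, which implies four strata. The list of strata is not in the available text, so this cannot be confirmed.

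**3. What late follow-up of responders alone can show.** The documents give no expected response rate, so it is an assumption, shown as a range. Its lower end, 20%, is the 1 of 5 or 2 of 10 that the plan calls worthy of further investigation. The 5% event rate is the top of the plan's own expectation. No other losses are assumed. With n patients in late follow-up:

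- chance of seeing at least one event at a true 5% rate: 1 − 0.95^n
- one-sided 95% upper bound if no event is seen: 1 − 0.05^(1/n)

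| Assumed response | n in late follow-up | Chance of at least one event | Upper bound, zero events |
|---|---|---|---|
| 20% | 45 × 0.2 = 9 | 1 − 0.95^9 = 37% | 1 − 0.05^(1/9) = 28% |
| 50% | 45 × 0.5 = 22.5, taken as 22 | 1 − 0.95^22 = 68% | 1 − 0.05^(1/22) = 13% |
| 80% | 45 × 0.8 = 36 | 1 − 0.95^36 = 84% | 1 − 0.05^(1/36) = 8.0% |
| All 45 kept | 45 | 1 − 0.95^45 = 90% | 1 − 0.05^(1/45) = 6.4% |

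For comparison, a stratum of 10, which the plan itself calls too small, gives 1 − 0.95^10 = 40% and 1 − 0.05^(1/10) = 26%. At 20% response, the late safety group of 9 is smaller than that.

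**4. Visits for those who stay.** After month 12, Required Observations continues chimerism testing only for patients infused for inadequate chimerism, and immunological tests only for strata II and III. Whether a clinical assessment is required in years 2 and 3 depends on which of the two texts a site follows.

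**The case against.** Several objections have weight.

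- **The period is a maximum.** A reader might infer that the plan promises every subject a full 3 years and that removal breaks the promise. The documents say up to 3 years, so early exit does not strictly breach them. What stands is that the exit depends on outcome, with no time and no safety provision.
- **The declared secondary endpoint is infusion toxicity.** No late-toxicity or chronic GVHD rate is a named analysis. That is correct. But related events are collected after day 30, the adverse-event frequency has no time window, and the hypothesis covers GVHD.
- **Removal may come only at 12 months.** This is a natural reading. The selection would then affect only the time after that, but it would still affect all of it.
- **Safety data as a whole do not come mainly from responders.** A reader might infer that they do. Treat 3 years as fixed, with 20% response and exit at 12 months: responders give 9 × 3 = 27 person-years and non-responders 36 × 1 = 36. The point concerns only the time after removal.
- **Later treatment confuses attribution.** A non-responder may receive another boost or transplant, and later GVHD may belong to that. This is a reason to date the later treatment and report subsequent events separately, not to stop recording.
- **Yearly visits may include an examination.** Section VI.7 says that patients are examined at required follow-up visits, so the gap after month 12 may be smaller in practice. The two texts still differ.
- **Some text was not available.** Pages just before the enrolment plan could not be read, and an off-study provision may be there.

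**Conclusion.** The point holds for late safety. As the available text stands, once non-response is declared, related events and GVHD would be captured only in responders, and the suspension rule might miss GVHD in a removed patient. If only responders remain, late follow-up falls from 45 patients to 9 at an assumed 20% response and to about 22 at 50%. The chance of seeing at least one event at a true 5% rate falls from 90% to 37% and 68%. These figures rest on the assumed response rates, on no other losses, and on removal ending all observation.

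A reader might go further and infer that late harm would be understated, because non-responders carry the same late risk. The documents give no late risk by response, so neither the equality nor the direction of any bias can be shown. The loss of information and the selection on outcome do not depend on it.

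**What to change.** In the enrolment plan, replace the removal sentence with wording to this effect: a patient without graft augmentation by a stated time point is recorded as a non-responder; treatment is left to standard procedures, as now; and the patient stays in safety data collection for the same period of up to 3 years as other subjects. That collection covers GVHD, related adverse events and vital status, and chart review is enough. Record the date and type of any later transplant or boost, and report events after it separately. In Statistical Analysis, state the denominator for late events.

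The sponsor should also reconcile the Schedule, which lists clinical assessment yearly up to 3 years, with Required Observations item 1, which lists it only to 12 months.

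The cost is an IRB-approved amendment and somewhat longer data collection on non-responders, some of whom may be treated elsewhere. Section VI.7 says that the planned testing is medically indicated regardless of participation, so the added burden on patients should be small.
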